However, the method of performing nerve blocks through surface anatomy localization has its drawbacks, including inaccurate positioning, low success rates, poor safety, and unsatisfactory outcomes. Some researchers argue that using the thyrohyoid membrane as a target for ultrasound-guided superior laryngeal nerve block can be challenging. Traditional ultrasound-guided superior laryngeal nerve block methods often rely on the thyrohyoid membrane and the superior thyroid artery as ultrasound landmarks, injecting local anesthetic solution beneath the thyrohyoid membrane and adjacent to the superior thyroid artery. However, locating the thyrohyoid membrane and the small superior thyroid artery can be extremely challenging, especially for beginners. Even experienced clinicians, despite their familiarity with anatomy and skill, can struggle to identify these structures under ultrasound. Therefore, there is a pressing need for simpler, more precise, and easier-to-locate methods of superior laryngeal nerve block in clinical practice.

In our preliminary research, while performing superior laryngeal nerve block, we observed that the injected solution could spread along the surface of the thyroid cartilage plate, extending towards the thyrohyoid membrane. Given that the solution could reach the superior laryngeal nerve from the surface of the thyroid cartilage, we propose that injecting

local anesthetic solution on the surface of the thyroid cartilage can effectively block the superior laryngeal nerve, a technique we refer to as "Thyroid Cartilage Plane Block." This method offers the advantage of easy identification of the thyroid cartilage under ultrasound, making it more convenient to perform than traditional methods. Therefore, this study aims to investigate the clinical effectiveness and safety of superior laryngeal nerve block through surface injection of local anesthetic solution on the thyroid cartilage in patients undergoing general anesthesia with endotracheal intubation.

Two: Research Objectives

1. Primary Objective: To evaluate the effectiveness of ultrasound-guided Thyroid Cartilage Plane Block for superior laryngeal nerve blockade.
2. Secondary Objectives: To assess the safety and ease of performance of ultrasound-guided Thyroid Cartilage Plane Block for superior laryngeal nerve blockade.

Three: Research Design, Methods, and Study Steps

1. Research Design

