Select patients undergoing elective awake tracheal intubation surgery and randomly assign them to two groups using a random number table. The control group will receive surface anesthesia of the throat using local anesthetic sprayed via fiberoptic bronchoscope, while the experimental group will undergo ultrasound-guided Thyroid Cartilage Plane Block.

The sample size for the study is determined based on the results of a pilot study. The primary outcome measure is the success rate of superior laryngeal nerve blockade. With a statistical power of $1-\beta=0.9$ and a significance level of $\alpha=0.05$, a sample size of $n=25$ is calculated. Assuming a dropout rate of 10%, the final sample size for each group is determined to be 30 cases.

2. Research Methods

The study will clinically evaluate the effectiveness, safety, and ease of performing Thyroid Cartilage Plane Block.

3. Study Steps

Select 60 patients undergoing elective awake tracheal intubation surgery.

Instruct patients to fast (no food or drink) for 8 hours before the procedure.

Upon admission to the operating room, monitor patients' ECG (electrocardiogram), BP (blood pressure), and SpO₂ (pulse oxygen saturation). Establish intravenous access in the upper extremities and administer normal saline solution. Administer a loading dose of dexmedetomidine at 0.5 µg/kg over 5 minutes, followed by an infusion at a rate of 0.3-0.6 µg/(kg·h) and intravenous injection of fentanyl at 0.1 µg/kg. Perform radial artery puncture and catheter placement for invasive arterial pressure monitoring. Use a computer-generated random number table to allocate patients into two groups in a 1:1 ratio. To ensure

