objectivity, a nurse not involved in the study prepares sealed opaque envelopes containing the group assignments. All patients are divided into the Thyroid Cartilage Plane Block Group (T Group) and the Control Group (C Group). Patients in the C Group receive airway surface anesthesia using the fiberoptic bronchoscope-guided local anesthetic spray method throughout the procedure. In the experimental T Group, ultrasound-guided bilateral Thyroid Cartilage Plane Block is performed using the thyroid cartilage plate as an anatomical landmark. Local anesthetic is injected on the surface of the thyroid cartilage plate. The blocking procedure is as follows: Use a Sonosite high-frequency linear array transducer (5-13 MHz, Sonosite, USA). Place the transducer parallel to the spine on one side of the neck, ensuring clear visualization of the thyroid cartilage plate under ultrasound. Employ ultrasound-guided in-plane or out-of-plane techniques to display the needle insertion path and tip. Once the needle tip contacts the upper half of the thyroid cartilage plate, inject 3 ml of 2% lidocaine on the surface of the thyroid cartilage plate (the dosage is consistent with the commonly used local anesthetic volume for classic superior laryngeal nerve block methods in clinical practice). Subsequently, perform fiberoptic bronchoscope-guided oropharyngeal, subglottic, and tracheal surface anesthesia. After completing surface anesthesia, select an appropriate-sized tracheal tube and perform fiberoptic bronchoscope-guided tracheal intubation, securing

it properly.

4. The research flowchart is as follows:

Four: Patient Selection

Inclusion Criteria: We will select 60 patients who meet the following criteria for inclusion in the study:

- Patients scheduled for awake tracheal intubation surgery under general anesthesia.
- Patients with difficult airways (e.g., limited cervical spine mobility, full stomach, partial airway obstruction, craniofacial deformities or trauma, micrognathia, mouth opening <3cm, Mallampati III or IV classification) posing challenges for mask ventilation or intubation.
- Age between 18 and 65 years.
- Gender is not restricted.
- ASA classification of I or II.

Exclusion Criteria: Patients meeting any of the following criteria will be excluded from the study:

- Cardiovascular dysfunction or arterial aneurysms.
- Mental or neurological disorders or concomitant arterial aneurysms.
- Infection at the puncture site.
- Allergy to local anesthetics.

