- Continuous use of antiplatelet or anticoagulant medications preoperatively.

- Hoarseness or coughing while drinking water.
- Bronchial asthma.
- Participation in other clinical trials within the previous 3 months before enrollment or current participation in other clinical trials.

3. Study Termination Criteria

The study may be terminated under the following circumstances:

- 1) Any medical condition or event occurs during the study that poses a potential risk to the continued participation of the research subjects.
- 2) Subjects receive anesthetic regimens other than the specified airway surface anesthesia rescue protocol, or if they are unable to complete the trial according to the study protocol for any reason.
- 3) The investigator determines that other circumstances warrant discontinuation from the trial.
- 4) Poor effectiveness of airway surface anesthesia, resulting in the patient's inability to tolerate awake tracheal intubation, or patient refusal to proceed.

Five: Alternative Diagnostic and Therapeutic Methods

In cases where the airway surface anesthesia is ineffective, and patients are unable to tolerate intubation, we will proceed with additional airway surface anesthesia using 2% lidocaine via a fiberoptic bronchoscope through an epidural catheter to enhance airway surface anesthesia.

Six: Assessment Parameters and Timing

Primary Outcome:

Record the comfort score immediately after intubation (5 points: resistance movement of the head or limbs; 4 points: verbal protest; 3 points: severe painful expression; 2 points: slight painful expression; 1 point: no response).

Secondary Outcomes:

1. Record the duration of the blocking procedure (from the start of ultrasound probe positioning to completion of drug administration).

2. Record the following parameters at specific time points (T0: upon entry to the operating room, T1: before insertion of the tracheal tube, T2: immediately after tracheal tube insertion, T3: 5 minutes after successful intubation):

- Mean Arterial Pressure (MAP)
- Heart Rate (HR)
- Ramsay Sedation Score (6 points: unarousable; 5 points: arousable but slow response to stimulation; 4 points: asleep but brisk response to stimulation; 3 points: asleep with a moderate response to command; 2 points: calm and cooperative with orientation; 1 point: anxious, restless, or agitated. Sedation satisfaction is defined as 2-4 points, while oversedation is defined as 5-6 points).

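### Does the absence of a recorded sedation time and dose in both arms undermine the comparison of comfort scores?

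*Protocol*

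**What the plan says.** Section Three (Study Steps) gives every patient a dexmedetomidine load of 0.5 µg/kg "over 5 minutes, followed by an infusion at a rate of 0.3-0.6" µg/(kg·h), with fentanyl and an arterial line. Allocation is written after these steps: "Use a computer-generated random number table to allocate patients into two groups in a 1:1 ratio".

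The arms then diverge. For the control group: "Patients in the C Group receive airway surface anesthesia using the fiberoptic bronchoscope-guided local anesthetic spray method throughout the procedure". The T group has a bilateral ultrasound-guided block, and then: "Subsequently, perform fiberoptic bronchoscope-guided oropharyngeal, subglottic, and tracheal surface anesthesia".

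Section Six names the primary outcome as "Record the comfort score immediately after intubation". Mean arterial pressure, heart rate and the Ramsay score are taken on entry to the operating room (T0) and at three later points: "T1: before insertion of the tracheal tube, T2: immediately after tracheal tube insertion, T3: 5 minutes after successful intubation". These points are set by events, not by time since sedation began, and they are not limited to one arm. The only duration listed is "Record the duration of the blocking procedure (from the start of ultrasound probe positioning to completion of drug administration", which section Seven repeats among the efficacy criteria. Section Six lists no spray time, infusion rate used, cumulative sedative dose or interval from sedation to intubation.

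The primary objective in section Two is "To evaluate the effectiveness of ultrasound-guided Thyroid Cartilage Plane Block for superior laryngeal nerve blockade". The secondary objectives are safety and ease of performance.

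**The concern.** An infusion already running at allocation continues through whatever airway preparation the arm requires. The T group has an extra step, so its patients may reach the tube after a longer infusion. Comfort is scored at tube insertion, and more sedation could plausibly improve it whether or not the block works. The permitted infusion rate also spans a factor of two with no stated rule for choosing it.

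The one procedure time that is listed cannot settle the matter, because it does not exist in the control group. If sedation times and pump totals are not written down at the bedside, no later analysis plan can recover them. At stake would be the attribution of a comfort difference to the block rather than to sedation. Ease of performance would also have no control value.

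**Working it through.** **Inputs from the Protocol (section Three).** Load 0.5 µg/kg; infusion 0.3 to 0.6 µg/(kg·h); 30 patients per group. No procedure durations are given, so all minutes below are assumptions.

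**1. Extra dexmedetomidine if the T group takes longer.** Extra dose = rate × extra minutes / 60.

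| Assumed extra minutes | At 0.3 | At 0.6 | Share of the 0.5 µg/kg load |
|---|---|---|---|
| 5 | 0.3 × 5/60 = 0.025 | 0.6 × 5/60 = 0.05 | 5–10% |
| 10 | 0.05 | 0.10 | 10–20% |
| 15 | 0.075 | 0.15 | 15–30% |

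**2. The same extra dose against the cumulative dose.** After an assumed 20 minutes of infusion, the cumulative dose is 0.5 + 0.3 × 20/60 = 0.60 µg/kg at the low rate and 0.5 + 0.6 × 20/60 = 0.70 µg/kg at the high rate. Ten further minutes add 0.05/0.60 = 8.3% or 0.10/0.70 = 14.3%. The load, written before allocation and identical in rule for both arms, makes up 0.5/0.60 = 83% or 0.5/0.70 = 71% of those totals.

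**3. The rate range.** The gap 0.70 − 0.60 = 0.10 µg/kg over 20 minutes is as large as the most that ten extra minutes can add. It is a spread between individual patients and open to both arms. Nothing in the text ties the rate to the arm.

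**4. Direction of the arm difference.** Difference in infusion time = block time + (T spray time − control spray time). The bracket may be negative: the control group is sprayed throughout, while the T group's later spray is described by region (oropharyngeal, subglottic, tracheal). Neither the sign nor the size of the total can be computed from the document.

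**5. From dose to comfort score.** One can compute how often a two-group ANOVA at 5% would reject if the block did nothing and sedation alone shifted comfort by *d* standard deviations (noncentral t, noncentrality *d* × √(n/2), 2n − 2 degrees of freedom). At n = 30 this gives 6.7% for *d* = 0.1 and 47.8% for *d* = 0.5. Nothing in the Protocol links 0.025 to 0.15 µg/kg to any value of *d*, so these figures do not measure the trial's risk. In addition, section Eleven assigns ANOVA to normally distributed continuous data and does not say how the 1-to-5 comfort score will be tested.

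**6. What is recorded in both arms.** The Ramsay score is taken at T0 to T3, with bands for satisfactory sedation (2–4) and oversedation (5–6). T1 falls just before the tube and T2 at the moment comfort is scored. Mean arterial pressure and heart rate accompany it. An imbalance large enough to matter clinically should be visible at T1, before the tube itself acts as a stimulus.

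**The case for a change.** The strongest case for a change is that the Ramsay score measures sedation state, not exposure. It is a coarse ordinal scale taken after allocation. A calmer T group at T1 could reflect better airway anesthesia or more drug, and the score cannot say which. Logging four times and a pump reading at T1 and T2 would cost almost nothing, and a missed reading cannot be recovered. If the arms matched on these, the sedation explanation would weaken.

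Part of this stands. Section Six does not list exposure, the Ramsay score is a check rather than a clean adjustment, and the block duration has no comparator.

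The step to a needed change does not follow. Section Six lists outcomes; it does not show what the case report form or the anesthetic record holds, so the text supports only that these items are not listed as outcomes. Nor would the extra data resolve attribution. Elapsed time arises after randomisation and, if the block lengthens it, is nearly collinear with arm. An adjusted analysis would be imprecise and only descriptive. Time spent delivering the block is part of the strategy being randomised, so block plus spray against spray alone remains a fair comparison; only the explanation of mechanism is limited.

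A duration defined for the T group alone still serves the ease objective as a description. Its repetition in section Seven is a matter of labelling.

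**Conclusion.** No change to the plan is needed. Section Six lists no sedative dose, rate or sedation-to-intubation time for either arm, and its only procedure duration applies to the T group. A difference in sedation around intubation can therefore be examined only through the Ramsay score, mean arterial pressure and heart rate at T1 and T2. That limits how finely a comfort difference can be explained; it does not bias the randomised comparison of the two strategies.

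The possible size is 0.025 to 0.15 µg/kg of extra dexmedetomidine, 5 to 30% of the load. This rests on an assumed 5 to 15 extra minutes in the T group that the Protocol does not establish, and the effect of such a dose on comfort is unknown. Investigators who wish to could report sedation times and cumulative dose by arm, and mark the block duration as T group only. This would be useful description, but it would change neither the primary result nor its validity.

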3. Record the number of cases with reduced voice tone before intubation.

4. Document patient coughing upon contact of the fiberoptic bronchoscope with the vocal cords before intubation (1 point: no response, 2 points: mild cough, 3 points: severe cough).
5. Assess the tolerance of the tracheal tube after successful intubation (3 points: strong resistance requiring immediate general anesthesia; 2 points: restlessness and mild resistance; 1 point: cooperative).
6. Record adverse reactions such as coughing and nausea/vomiting during intubation.
7. Document post-extubation throat pain, voice tone reduction, and voice tone reduction at 24 hours post-operation.
8. Assessment of superior laryngeal nerve blockade effectiveness based on clinical diagnostic criteria:
 - Inability to produce high-pitched sounds, monotone voice.
 - Morphological changes in the vocal cords observed during laryngoscopy (e.g., irregular vocal cord surface, wrinkles, malposition, reduced mobility).
 - Absence of neural reflex upon touching the mucosa above the vocal cords.
 - Meeting two of the above diagnostic criteria indicates successful superior laryngeal nerve blockade.
9. Record adverse reactions such as local anesthetic toxicity, local hematoma at the puncture site, and infections.

10. Record patient satisfaction.

Seven: Efficacy Assessment Criteria

- Record the duration of the blocking procedure (from the start of ultrasound probe positioning to completion of drug administration).
- Ramsay Sedation Score (6 points: unarousable; 5 points: arousable but slow response to stimulation; 4 points: asleep but brisk response to stimulation; 3 points: asleep with a moderate response to command; 2 points: calm and cooperative with orientation; 1 point: anxious, restless, or agitated. Sedation satisfaction is defined as 2-4 points, while oversedation is defined as 5-6 points).
- Patient coughing upon contact of the fiberoptic bronchoscope with the vocal cords before intubation (1 point: no response, 2 points: mild cough, 3 points: severe cough).
- Comfort score immediately after intubation (5 points: resistance movement of the head or limbs; 4 points: verbal protest; 3 points: severe painful expression; 2 points: slight painful expression; 1 point: no response).
- Tracheal tube tolerance after successful intubation (3 points: strong resistance requiring immediate general anesthesia; 2 points: restlessness and mild resistance; 1 point: cooperative).

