This clinical research will adhere to ethical principles and requirements outlined in the World Medical Association's "Declaration of Helsinki" and the regulations set forth by the National Health and Family Planning Commission of the People's Republic of China, including the "Ethical Review Measures for Biomedical Research Involving Human Subjects." Specific measures will include informed consent, privacy protection, free participation in research, risk control, protection of special subjects, and

compensation for research-related harm. Prior to commencing the study, the research protocol must receive approval from the ethics committee. Before enrollment, every subject will be provided with comprehensive information about the study's purpose, procedures, and potential risks. They will sign a written informed consent form. Subjects will be informed that participation in the clinical research is entirely voluntary, and they have the right to refuse or withdraw from the study at any stage without discrimination or retaliation. Their medical treatment and rights will not be affected. Informed consent forms will be retained as part of the clinical research documents, ensuring the protection of subjects' personal privacy and data confidentiality.

References

[2] Farzi Farnoush, Haddadi Soudabeh, Ebrahimpour Neda, et al. A Survey on the Effect of Oral Gabapentin on Hemodynamic Changes During Direct Laryngoscopy and Tracheal Intubation and Intraoperative Bleeding in Patients Undergoing Septorhinoplasty. *2015*,5(5):e29705.

[3] Chen Y, Jiang C. Clinical Application Progress of Internal Branch Block of Superior Laryngeal Nerve. *Chinese Continuing Medical*

Education, 2019, 11(35): 125-127.

[4] Fowler J G, VanEenenaam Jr D P, Johnson K N, et al. Single midline injection for bilateral superior laryngeal nerve block[J]. Journal of Clinical Anesthesia, 2020, 66: 109922-109922.

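### No MAP or heart-rate reading is scheduled between room entry (T0) and just before tube insertion (T1), so a brief fall after the block can go unrecorded and the only baseline precedes sedation

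*Protocol*

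**What the plan says.** Protocol Section Six, secondary outcome 2, lists four time points for MAP, heart rate and Ramsay score. The first two are "T0: upon entry to the operating room, T1: before insertion of the tracheal tube" and the last two are "T2: immediately after tracheal tube insertion, T3: 5 minutes after successful intubation".

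Section Three, Study Steps, gives the order of events after the patient enters the room:

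- ECG, blood pressure and SpO₂ monitoring and intravenous access.
- Sedation: "Administer a loading dose of dexmedetomidine at 0.5 µg/kg over 5 minutes", then a maintenance infusion within a stated range, and fentanyl.
- "Perform radial artery puncture and catheter placement for invasive arterial pressure monitoring".
- Allocation: "Use a computer-generated random number table to allocate patients into two groups in a 1:1 ratio".
- Bilateral block followed by bronchoscopic spray in the T group; spray alone in the C group.
- Intubation.

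Section Two makes the safety of the block a secondary objective. Section Six, item 9, reads: "Record adverse reactions such as local anesthetic toxicity, local hematoma at the puncture site, and infections". Item 6 covers reactions during intubation, with coughing and nausea or vomiting as examples. Neither item names a hemodynamic event. Section Ten asks for every adverse event to be recorded. Section Eleven compares groups by ANOVA for continuous data and names no baseline covariate.

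**The concern.** The interval that matters most for a hemodynamic reaction to the injection lies between the needle and the start of intubation. The schedule samples that interval only at its end. If MAP or heart rate drops after the block and recovers before T1, or if stimulation from the spray lifts it again, the planned tables show nothing. The control arm cannot repair this, because it lacks the same reading.

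The second issue is the baseline. T0 is taken before the sedative, the opioid and the arterial line, so it describes a patient in a different state from the one who receives the block or the spray. It is the only value measured before treatment, and hence the only one available for adjustment. An analysis plan can choose its covariates, but it cannot use a reading that was never taken. This is why the point belongs in the protocol.

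At stake are the sensitivity of one secondary safety outcome and some precision in the MAP and heart-rate comparisons. The primary outcome is not affected.

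**Working it through.** The document states no figure on this point that could be reproduced. The check has three parts.

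**1. Order of events.** Setting Section Six against the Study Steps gives: T0 → sedation load, infusion and fentanyl → arterial line → allocation → block (T only) → spray → T1 → tube → T2 → T3. T1 is fixed only as preceding the tube. Since spray is completed before intubation, a T1 after the spray is the natural reading. No reading falls between sedation and block, or between block and spray.

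**2. Is the comparison at T1 biased by sedation?** Write the mean at T1 as:

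- T arm: baseline + sedation + block and spray
- C arm: baseline + sedation + spray

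Baseline is balanced by randomization and the sedation regimen is common, so both drop out of T − C. What remains is block plus spray against spray alone. A simulation confirms it: 30 per arm, 5,000 runs per setting, with an assumed baseline SD of 12 mmHg, residual SD of 8 mmHg and a sedation effect that varies between patients. These inputs illustrate the logic and are not estimates for this trial.

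| Common sedation effect (mmHg) | Mean T − C, no block effect | Rejection rate | Mean T − C, true effect −8 | Power |
|---|---|---|---|---|
| 0 | −0.05 | 5.0% | −8.08 | 57% |
| −10 | 0.04 | 5.3% | −8.02 | 55% |
| −20 | −0.07 | 4.6% | −7.97 | 49% |

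The estimate stays on target and the error rate stays near 5%. Varying response to sedation costs only some power.

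Cancellation needs similar sedation exposure at T1 in both arms. The infusion may run anywhere from 0.3 to 0.6 µg/kg/h. If one arm ran at the top of the range and the other at the bottom for an assumed 10 to 30 minutes, the gap would be 0.3 × 10/60 = 0.05 to 0.3 × 30/60 = 0.15 µg/kg. That is 10% to 30% of the 0.5 µg/kg load. It is an upper bound and needs a systematic difference between arms.

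**3. What would a post-sedation baseline add?** The detectable difference in SD units is (z₀.₉₇₅ + z_power) × √(2/n), multiplied by √(1 − ρ²) when a baseline with correlation ρ to T1 is a covariate. With n = 30 per arm (Section Three) and two-sided alpha 0.05 (sidedness is not stated, so assumed):

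- 80% power: (1.960 + 0.842) × √(2/30) = 0.72 SD
- 90% power: (1.960 + 1.282) × √(2/30) = 0.84 SD

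| Assumed ρ | 80% power | 90% power |
|---|---|---|
| no covariate | 0.72 | 0.84 |
| 0.3 | 0.69 | 0.80 |
| 0.5 | 0.63 | 0.73 |
| 0.7 | 0.52 | 0.60 |

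If the planned 10% dropout leaves 30 × 0.9 = 27 per arm, the 80% figures are 2.802 × √(2/27) = 0.76 SD without a covariate and 0.76 × √0.75 = 0.66 SD at ρ = 0.5.

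The correlations are assumptions. Against an analysis that already adjusts for T0, the gain is smaller and depends on how much better the post-sedation value predicts T1 than T0 does.

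**The case against.** The strongest defense is the design itself. Both arms get the same sedation before allocation, and the planned analysis compares groups. A reader might infer that the block's effect cannot be separated from dexmedetomidine. The documents do not support that: it would be true only of a change from T0 to T1 within the T arm, and the protocol nowhere makes that change an outcome. The same answer covers a cuff reading at T0 against an arterial-line reading later. The protocol does not say which device supplies MAP, and any device difference would be common to both arms. This part of the defense stands in full.

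A reader might also infer that the trial would miss hypotension and bradycardia altogether, and that the protocol's own literature warns of them. Neither follows. A sustained fall would still be present at T1. ECG and invasive pressure are running before the block, Section Ten covers all adverse events, and items 6 and 9 are open lists. The supposed warning is the title of reference 5, "Hypotension and bradycardia following superior laryngeal nerve block", which the body text never cites. It gives no frequency, severity or timing, and nothing at hand shows that such reactions are brief.

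The defense does not reach the transient fall. Having a monitor on display does not mean that a value is written down. Section Ten gives no indication of which pressure or rate change counts as an event, so recording rests on individual judgement, between two visibly different procedures. The flowchart is not visible in the available text and the record form is not shown. Either might add a reading, but Section Six as written does not.

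A last fair objection concerns the remedy. Extremes recorded from the first airway step up to T1 would probably cover a longer time in T (block plus spray) than in C (spray alone). Longer windows yield more extreme values by chance and would count against the block. That is correct, and the window must therefore be of equal length.

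**Conclusion.** The point holds as a minor design gap with a cheap improvement. The schedule cannot show a fall in MAP or heart rate that follows the block and resolves before T1, and its only pre-treatment reading precedes sedation. The randomized comparison at T1 is unbiased with respect to sedation, provided that infusion rates and the time from load to T1 do not differ systematically by arm. Block safety can still be assessed, with less sensitivity to brief events.

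How many transient falls would be lost cannot be stated, because the document gives no rate or duration. The precision gain is from 0.72 SD to 0.63 SD at 80% power if the post-sedation baseline correlates 0.5 with T1, within a range of 0.69 to 0.52 SD for correlations of 0.3 to 0.7. In variance terms, ρ = 0.5 is worth 30 / (1 − 0.25) = 40 patients per arm without a covariate. These figures assume two-sided 5% alpha, 30 analysed per arm and the normal approximation.

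**What to change.** Three additions to Section Six:

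1. **A new baseline reading.** Take MAP and heart rate after the sedation load and arterial line and before the envelope is opened. Use it as the baseline covariate for group comparisons at T1 to T3. Because it precedes allocation, treatment cannot affect it.
2. **Extremes over an equal window.** Record the lowest and highest MAP and heart rate over a window of the same fixed length in both arms, starting at the first airway anesthesia step (block in T, spray in C). The sponsor should choose a length that normally ends before tube insertion in either arm, so that the response to intubation does not enter the maximum.
3. **Named events.** Add hypotension and bradycardia to item 9, with definitions set by the sponsor and recorded in the same way in both arms.

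The cost is a few lines of protocol text and a few extra fields on the record form. The monitors are already running in every patient, so no new procedure is needed.
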